7.1.6. Analysis of oxygen saturation and arterial blood gas

It is recommended but not required to conduct arterial blood gas analysis at screening, and during the treatment / follow-up observation periods according to clinical needs.

7.1.7. Pregnancy test

Only for women of childbearing age, under 54 years old, during the screening period.

7.1.8. ECG

During the screening period (up to 72 hr prior to screening is allowed), treatment / follow-up observation period. On the drug administration day (Day 1), ECG should be done before drug infusion and 2 hrs after drug infusion. ECG should be done in visit D8 and D15, if patient is still in hospital.

7.1.9. Chest X-ray or CT scan

It is recommended but not required to have Chest X-ray or CT scan during the screening period. Imaging study that has been done up to 72 hr prior to screening is allowed in lieu of screening. During the treatment / follow-up observation period, the doctor can determine the number and time of chest image study.

7.1.10. SARS-CoV-2 Viral nucleic acid check

Positive viral tests that have been done prior to screening are allowed in lieu of screening. If the investigator conducts an unscheduled visit to the viral nucleic acid test, the data results must be recorded in the CRF. The follow up viral nucleic acid tests are optional.

7.1.11. Cytokine and lymphocyte subtype detection (For selected sites only)

If conditions permit, a 5 ml blood sample should be collected and separated into plasma and PBMC. The samples can be frozen and stored for research purposes. Plasma samples are for testing of inflammatory cytokines (IL-1 β , IL-6, TNF- α , MIP α , INF- γ , IP10, MCP, GCSF, IL-10). The PBMC are for testing lymphocyte subtypes and activation/exhaustion markers (flow cytometry detection analysis: CD3 / CD4 / CD8 / PD1 / Tim3, etc.) at D1 before IV infusion, D4, D8 and D15.

7.1.12. Evaluation of clinical status

Clinical status should be evaluated and recorded daily when the patient is hospitalized. The screening period must assess the clinical status and recorded as baseline.

If the patient clinical status improves and is discharged to home care, the follow up visits should follow the study schedule ([Table 2](#)), and the visits can be carried out through telemedicine (phone or video interviews). The clinical investigators should make best effort to obtain the vital signs, clinical status evaluation, concomitant medicines and adverse events assessment. The laboratory tests, radiology study, ECG and research samples are optional.

7.2. **REQUIRED OBSERVATIONS (STUDY CALENDAR as in Synopsis)**

7.2.1. **Screening period**

Visit 1

- Sign the informed consent by patient or by a legally authorized representative;
- Record the past medical history;
- Collect demographic data;
- Record vital signs and physical examination;
- Laboratory tests should be done according to Section 7.1.5. Tests done 72 hrs prior to screening are allowed;
- Record digital oxygen saturation;
- Arterial blood gas analysis (optional, tests done 72 hrs prior to screening are allowed);
- Pregnancy check (women only, under 54 years old);
- ECG. Tests done 72 hrs prior to screening are allowed;
- Chest CT scan or X-ray. Tests done 72 hrs prior to screening are allowed;
- Detection of SARS-CoV-2 viral nucleic acids. Prior positive viral results are allowed;
- Clinical status assessment;
- Collect blood samples for serum cytokines and lymphocyte subtypes (selected sites only);
- Confirm the inclusion / exclusion criteria;
- Record concomitant medications.

7.2.2. **Treatment / follow-up observation period (D1 ~ D29)**

Visit 2 (D1)

- Record vital signs before study drug infusion and at 60±10 minutes after the start of drug infusion;
- Confirm the inclusion / exclusion criteria;
- Subject is randomized;
- Chest CT examination (optional);
- Record digital oxygen saturation;
- Arterial blood gas analysis (optional);

- Laboratory tests according to Section 7.1.5;
- ECG before drug infusion, and at 2 hrs (120 ± 15 min) after drug infusion;
- Study drug administration;
- Clinical status assessment;
- Record IMV / NIV, ECMO, or oxygen therapy;
- Collect blood samples for serum cytokines and lymphocyte subtypes (selected sites only);
- Record adverse events and concomitant medications.

Visit 3 (D4 \pm 2d)

- Record vital signs;
- Clinical status assessment;
- Chest CT scan (optional);
- Record digital oxygen saturation;
- Arterial blood gas analysis (optional);
- Laboratory tests: CBC, blood biochemistry, C-reactive protein;
- Collect blood samples for serum cytokines and lymphocyte subtypes (selected sites only);
- Record adverse events and concomitant medications.

Visit 4 (D8 \pm 2d)

- Record vital signs;
- Laboratory tests: CBC, blood biochemistry, C-reactive protein, coagulation tests;
- Chest CT scan (optional);
- Record digital oxygen saturation;
- Arterial blood gas analysis (optional);
- ECG;
- Clinical status assessment;
- Record IMV / NIV, ECMO, or oxygen therapy;
- Collect blood samples for serum cytokines and lymphocyte subtypes (selected sites only);
- Record adverse events and concomitant medications.

Visit 5 (D15 ± 2d)

- Record vital signs;
- Laboratory tests: CBC, blood biochemistry, C-reactive protein; coagulation tests;
- Chest CT scan (optional);
- Record digital oxygen saturation;
- Arterial blood gas analysis (optional);
- ECG;
- Clinical status assessment;
- Record IMV / NIV, ECMO, or oxygen therapy;
- Collect blood samples for serum cytokines and lymphocyte subtypes (selected sites only);
- Record adverse events and concomitant medications.

Visit 6 (D29 ± 3d)

- Record vital signs;
- Detection of SARS-CoV-2 viral nucleic acids if the D15 test is positive;
- Clinical status assessment;
- Record IMV / NIV, ECMO, or oxygen therapy;
- Record adverse events and concomitant medications.

If the patient clinical status improves and is discharged to home care, the follow up visits can be carried out through telemedicine (phone or video interviews). The clinical investigators should make best effort to obtain the vital signs, clinical status evaluation, concomitant medicines and adverse events assessment. The laboratory tests, radiology study, ECG and research samples are optional.

8. ADVERSE EVENTS AND SERIOUS ADVERSE EVENTS

8.1. Adverse Events

8.1.1. Definition of Adverse Events

Adverse event means any untoward medical occurrence associated with the use of an intervention in humans, whether or not considered intervention-related. Since the clinical study has the target population as hospitalized patients with COVID-19 diagnosis and requiring oxygen support, the Grade III to V adverse events will be collected and reported in this study.

8.1.2. Definition of Serious Adverse Events (SAE) in COVID-19

An adverse event (AE) or suspected adverse reaction is considered "serious" if, in the view of either the investigator or sponsor in this COVID-19 clinical trial, it results in any of the following outcomes: death, or a life-threatening adverse event other than COVID-19 progression that requires admission to the ICU, or organ failures in addition to COVID-19 respiratory failure.

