1.7. Clinical Experience of CD24Fc in Humans

1.7.1. Phase I Summary:

OncoImmune Inc. has developed and manufactured clinical grade CD24Fc for use in humans. CD24Fc has been tested in a Phase I clinical trial in healthy human subjects, and this study showed preliminary safety of single dose CD24Fc by IV administration. A total of 40 subjects were randomized in 5 cohorts of 8 subjects, and 39 subjects completed the study. CD24Fc was administered via IV infusion over 1 hour at doses ranging from 10 to 240 mg, and the subjects were followed over a six-week period. A MTD was not encountered.

In general, adverse events were mild to moderate in severity. The most common AEs were headache (6 [15.0%] subjects), accidental burns second degree (3 [7.5%] subjects), non-sustained ventricular tachycardia (2 [5.0%] subjects), and upper respiratory tract infection (2 [5.0%] subjects). The rates of the AEs were similar in the placebo control group. The SAE of ventricular tachycardia was considered mild in severity by the investigator and did not lead to discontinuation of the subject from the study. This SAE was considered to be drug related due to its close temporal proximity to dosing, though similar short, isolated episodes of non-sustained ventricular tachycardia may be seen in up to 4% of normal, healthy populations. No deaths or adverse events leading to discontinuation occurred during the study.

1.7.2. Phase IIa Summary:

A Phase IIa prospective randomized double-blind clinical trial of CD24Fc for acute GVHD prophylaxis in myeloablative matched unrelated donor HCT was initiated in July 2016. The first patient was enrolled in Sept 2016. A total of 24 patients were enrolled in three cohorts, 240mg single dose given at day -1, 480mg single dose at day -1, 480-240-240mg multi-dose given on day -1, day 14 and day 28, with 6 patients receiving CD24Fc and 2 patients receiving placebo in each cohort. The last patient was enrolled in Dec 2017. The last patient reached one year post-HCT in December 2018. Data was locked and the final clinical study report (CSR) was submitted to FDA in April 2019. In total there are 18 patients in the CD24Fc group and 6 patients in the placebo group (3:1 randomization). All planned dosages were delivered on schedule.

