1.7.2.2. Phase IIa Clinical Study Summary

Overall, CD24Fc was well tolerated in the Phase IIa study. There were no infusion-related toxicities. There was one possible drug related treatment emergent adverse event (TEAE) of \geq grade III-IV hyperglycemia in the 480 mg CD24Fc group, which was managed with insulin. One dose-limiting toxicity (DLT) was observed in the placebo group, and no DLTs were observed in the CD24Fc group. There were no adverse events leading to death in subjects administered CD24Fc within the 180 days. There was one adverse event of pneumonia that led to the death of a subject at Day 48 in the placebo group. The development of anti-drug antibodies (ADA) were not detected in any of the 24 subjects at any point out to day 100 after HCT.

The most common TEAEs \geq grade III ($> 10\%$) included a decrease in platelet counts (83.3% placebo and 94.4% CD24Fc), decrease in WBC counts (66.7% placebo and 88.9% CD24Fc), decrease in neutrophil counts (50% placebo and 83.3% CD24Fc), decrease in lymphocyte counts (50% placebo and 77.8% CD24Fc), anemia (50% placebo and 66.7% CD24Fc), stomatitis (83.3% placebo and 50% CD24Fc), and nausea (0% placebo and 11.1% CD24Fc). These are expected SAEs were anticipated as they were hematologic in nature and were otherwise considered related to the myeloablative conditioning regimen of HCT.

In the Phase IIa study, compared to treatment with placebo, treatment with CD24Fc resulted in trends toward:

1. Higher Grade III to IV acute GFS rate at Day 180 (94.4% in CD24Fc treatment group, 50.0% in placebo) (hazard ratio = 0.1),
2. Higher DFS rate at 1 year (83.3% in CD24Fc treatment group, 50.0% in placebo) (hazard ratio = 0.2),
3. Higher OS rate at 1 year (83.3% in CD24Fc treatment group, 50.0% in placebo) (hazard ratio = 0.2),
4. Higher Grade III to IV acute GRFS rate at Day 180 (83.3% in CD24Fc treatment group, 33.3% in placebo) (hazard ratio = 0.2),
5. Lower incidence of Grade III-IV acute GVHD by Day 180 (5.6% in CD24Fc treatment group, 33.3% in placebo) (hazard ratio = 0.1),
6. Lower cumulative incidence of leukemia relapse at 1 year (11.1% in CD24Fc treatment group, 33.3% in placebo) (hazard ratio = 0.3),
7. Lower incidence of non-relapse mortality at 1 year (5.6% in CD24Fc treatment group, 16.7% in placebo) (hazard ratio = 0.3),

8. Similar cumulative incidence of Grade II to IV acute GVHD by Day 180 (38.9% in CD24Fc treatment group, 33.3% in placebo) (hazard ratio = 2.6),

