1.8. Safety in Humans

1.8.1. Phase I Safety Data

A Phase I, randomized, double-blind, placebo-controlled, single ascending dose study to assess the safety, tolerability, and PK of CD24Fc in healthy male and female adult subjects was conducted. Details are also provided in section 3.8 A total of 40 subjects were randomized in 5 cohorts of 8 subjects each, and 39 subjects completed the study. CD24Fc was administered via IV infusion over 1 hour. In total, 18 (45.0%) subjects had a treatment-emergent adverse event (TEAE) during the study: 6 (60.0%) subjects in the placebo group, 2 (33.3%) subjects in the CD24Fc 10 mg group, 3 (50.0%) subjects in the CD24Fc 30 mg group, 2 (33.3%) subjects in the CD24Fc 60 mg group, 3 (50.0%) subjects in the CD24Fc 120 mg group, and 2 (33.3%) subjects in the CD24Fc 240 mg group.

All TEAEs in the study were considered mild to moderate in severity by the Investigator except for 1 subject in the placebo group who experienced a severe headache. The most common TEAEs were headache (6 [15.0%] subjects), burns second degree (3 [7.5%] subjects), non-sustained ventricular tachycardia (2 [5.0%] subjects), and upper respiratory tract infection (2 [5.0%] subjects).

Overall, 5 (12.5%) subjects had a study drug-related TEAE: 1 (10.0%) subject in the placebo group, 2 (33.3%) subjects in the CD24Fc 10 mg group, 1 (16.7%) subject in the CD24Fc 30 mg group, and 1 (16.7%) subject in the CD24Fc 60 mg group. The study drug-related TEAEs during the study were headache (4 [10.0%] subjects) and ventricular tachycardia (1 [2.5%] subject). A drug-related SAE of ventricular tachycardia was experienced by 1 subject in the CD24Fc 60 mg group. This SAE occurred at a rate comparable with normal populations, was considered mild by the Investigator, and did not lead to discontinuation from the study. No subjects died during the study and no subjects discontinued from the study due to an adverse event. There were no clinically meaningful changes from baseline in laboratory parameters, vital signs, ECGs, or physical exams during the study.

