Here we provided the strong evidence from pre-clinical data from in vitro cell culture, humanized mouse HIV model, and nonhuman primate model of SIV viral pneumonitis, the safety and efficacy in clinical proof-of-concept studies, and the pathogenesis of COVID-19 to support the clinical study in testing the safety and efficacy of CD24Fc as an immunomodulator in COVID-19 treatment. Based on the clinical experience and pharmacokinetic data of CD24Fc, we plan to give a single dose of 480 mg CD24Fc to eligible patients with confirmed COVID-19 and severe pneumonia. This dose is deemed safe as 32 HCT patients have been exposed to this or higher doses. The only drug-related SAE is a transient hyperglycemia in 1 patient that responded well to insulin treatment. Furthermore, based on in vitro effect of IFN γ inhibition and PK in HCT patients, a single dose should be sufficient to provide adequate drug concentration during the study period of two weeks.

All patients should have best available treatment according to local institutional guideline in US. It is recommended to follow the WHO Interim Guidance on Clinical Management of Severe Acute Respiratory Infection (SARI) When COVID-19 is Suspected (version 1.2, Mar. 13, 2020).

1.12. **Rationale for a Randomized, double blind, placebo-controlled Phase III Trial**

The Phase 1, Phase IIa and Phase II expansion cohort studies suggest that CD24Fc is safe and well tolerized in healthy people and in patients with hematological malignancies heavily treated with chemotherapy and radiation.

This multicenter Phase III clinical trial will evaluate adding CD24Fc to best available treatment for the efficacy in increase the proportion of patients from severe COVID-19 to convert to mild or moderate COVID-19. The randomized, double blind and placebo-controlled study will provide the most rigorous analysis to assess the efficacy of the novel biological agent CD24Fc in COVID-19 treatment.

1.13. **Pharmacological study in dose selection**

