8.1.3. Criteria for Determining the Severity of Adverse Events

AEs not listed in the CTCAE 5.0 version table can be classified into grades 1-5 with reference to the following table.

Grade	CTCAE
1	Asymptomatic or mild; only clinical or diagnostic observations; no intervention required
2	Moderate: Small, local, or non-invasive measures are required; age-related instrumental daily life activities (ADL) are limited *.
3	Serious or medically significant but not immediately life-threatening: hospitalization or lengthening of hospital stay required; disability, limited autonomic ADL **.
4	Life-threatening: urgent measures are needed. Intervention indicated to prevent permanent impairment, persistent disability or death.
5	deaths related to adverse events

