10.5. Interim Analysis and Stopping Rules

This study will establish an independent Data and Safety Monitoring Board (DSMB) for interim analysis. The composition, task responsibilities and implementation details of DSMB will be specified in the DSMB charter.

Two blinded safety reviews will be performed, respectively, when 50% and 75% of the planned enrollment has occurred with follow-up time reaching D15 and mortality data are available.

The study will also include an interim analysis at 70% of the required 146 events. The final analysis will be carried out after all 270 subjects have been randomized, dosed and completed the study.

In the interim analysis, the DSMB will re-estimate the sample size to determine whether it supports increasing the number of clinical improvement event targets. Chen's method will be used to re-estimate the sample size (37).

Safety reviews and stopping rules

The study have two blinded safety reviews respectively, when 50% and 75% of the planned enrollment has occurred with follow-up time reaching Day 15 and SAE data are available. DSMB will be provided with list of SAE including mortality and may unblind the data at its discretion to evaluate the balance of SAE in the two study arms.

Stopping rules

If the DSMB found that SAE is significantly higher in the CD24Fc arm, it may recommend termination of the trial after review of potential benefit of the study drug by unblinding all study subjects. Sponsor will make final decision based on the recommendation of DSMB.

Sample Size Re-Estimation

The interim analysis for the primary endpoint only will be performed after reaching 146 events (70% of information). A sample size reassessment of efficacy will be performed.

There sample size re-estimation 146 events will be based on preliminary data that are not 100% source-verified. The method will be based on Chen et al as stated in the protocol. If the conditional power is < 50% or >85%, the trial will continue without a sample size increase; whereas if the conditional power is between 50% to 85%, the sample size will be re-calculated to

have 85%. To maintain trial integrity, the DSMB will pick a sample size in a nearest interval with 5 patients. For example, if the re-estimated sample size is 287, the DSMB could pick any number in the interval of 285 to 289. Also, the maximum increased sample size will not be more than 70 patients above what is needed to observe 208 events.

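### The SAE definition in Section 8.1.2 omits non-COVID readmission or prolonged stay, disability and medically important events, so these fall outside the DSMB's SAE list, the SAE-based stopping guideline and immediate reporting

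*Combined protocol and SAP*

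**What the plan says.** Section 8.1.2 makes an event serious if "it results in any of the following outcomes: death, or a life-threatening adverse event other than COVID-19 progression". In full, the three listed outcomes are "death, or a life-threatening adverse event other than COVID-19 progression that requires admission to the ICU, or organ failures in addition to COVID-19 respiratory failure". The investigator or the sponsor may make the judgement, but only about these outcomes.

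Section 8.1.3 grades severity for events that have no entry in CTCAE version 5.0. Its Grade 3 description reads "Serious or medically significant but not immediately life-threatening: hospitalization or lengthening of hospital stay required; disability".

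The SAE definition is used in four places:

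- Section 10.5, safety reviews: "DSMB will be provided with list of SAE including mortality". The reviews take place when 50% and 75% of planned enrollment has reached Day 15.
- Section 10.5 and the Synopsis (Stopping Guidelines): the harm guideline is a significantly higher SAE frequency in the CD24Fc arm.
- Section 8.3: SAEs go to the sponsor immediately. Under Section 8.2, non-serious events are reported in a timely manner, and treatment-emergent events are summarised when the study is complete.
- Section 10.4.4: SAEs are summarised by arm.

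Sections 8.1.1, 8.1.6 and 8.2 limit adverse event collection to Grade III and above. One sentence in 8.1.6 names SAEs alongside those grades. Section 11.5 says the CRO's safety reports also go to the DSMB, without saying what they contain.

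**The concern.** A narrow definition is understandable when every patient is already in hospital with severe disease. The usual hospitalization criterion would otherwise pick up the illness under study. The list, however, removes hospitalization, disability and medical importance altogether, including when the cause has nothing to do with the course of COVID-19.

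This matters for detecting harm. CD24Fc is an immunomodulator and may be given alongside IL-6/IL-6R antagonists (Sections 3.1 and 6.4). The eligibility criteria in Section 4.2 do not exclude infection or sepsis. After discharge, visits may be remote, with laboratory tests and ECG optional (Section 7.1.12). Readmission for a new problem is then one of the clearer harm signals left, and it is not an SAE. If the drug increased such events without increasing deaths, intensive care admissions or organ failures, the SAE comparison that drives the stopping guideline would not show it.

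**Working it through.** The plan states no figure on this point, so there is nothing to reproduce. The check sets the definition against kinds of event, follows it through its uses, and then applies it to the earlier SAEs.

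**Step 1. Apply the three criteria.** Take events not due to COVID-19 progression, not life-threatening, and not judged to be an organ failure.

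| Event | Death | Life-threatening, needing ICU | Additional organ failure | SAE under 8.1.2? |
|---|---|---|---|---|
| Readmission or longer stay, e.g. a new bacterial infection treated on a ward | No | No | No | No |
| Event leaving lasting disability | No | No | No | No |
| Medically important event with none of the above | No | No | No | No |

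The next section, in its Grade 3 wording, uses the word serious for events of the first two kinds and puts medically significant events beside them.

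**Step 2. Follow the consequence.** An event in any of these rows is missing from the SAE list at both reviews, which fall at 0.50 × 270 = 135 and 0.75 × 270 = 202.5 (about 203) patients reaching Day 15. It does not count in the SAE comparison behind the stopping guideline. It is not immediately reportable. If it is Grade III or above, it is recorded and sent to the sponsor as non-serious. If it is below Grade III, nothing requires it to be recorded, because only SAE status could bring it in through the sentence in 8.1.6.

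**Step 3. Apply the definition to earlier drug-related SAEs.**

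- Phase I (Section 1.8.1): "A drug-related SAE of ventricular tachycardia was experienced by 1 subject in the CD24Fc 60 mg group". Section 1.7.1 adds: "The SAE of ventricular tachycardia was considered mild in severity by the investigator and did not lead to discontinuation". The event was not fatal, not life-threatening and not an organ failure, so it meets none of the three criteria. Being mild, it would also fall below the Grade III collection threshold.
- HCT patients (Section 1.11): "The only drug-related SAE is a transient hyperglycemia in 1 patient that responded well to insulin treatment". Section 1.7.2.2 describes "grade III-IV hyperglycemia in the 480 mg CD24Fc group, which was managed with insulin". No death, organ failure or ICU admission is mentioned, so on these facts it very likely meets none. Grade IV (life-threatening) is not excluded, however. The ICU clause in 8.1.2 could also be read as qualifying COVID-19 progression rather than the adverse event, and on that reading a Grade IV event would count without ICU admission.

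**Step 4. Size.** The documents give no rate of non-COVID readmission, disability or medically important events in this population. The 78% in Section 10.1 is a recovery rate, and recovery is a score of 5 or above, which includes patients still in hospital. It cannot serve as the number discharged and at risk of readmission. The size is therefore structural: three kinds of event are left out of every use of the definition.

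**The case against.** **The narrowing is deliberate.** Section 8.1.2 is headed as specific to COVID-19, and 8.1.1 explains that collection is adapted to patients already in hospital on oxygen. This justifies keeping expected disease course off the list. It does not justify leaving out readmission, disability or important events from other causes.

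**The DSMB has other sources.** A reader might infer that the DSMB would never see these events. The documents do not support that. CRO safety reports go to the DSMB (Section 11.5), the Synopsis has the CRO share safety data with it, and details are left to a charter that is not among the documents. There are also weekly safety teleconferences, monthly review by the Medical Monitor and sponsor, the Medical Monitor's power to stop the study (8.3), and the general grounds for suspension in 11.2. This objection stands against the absolute claim. It does not fill the gap, because no section says that any of these sources gives the DSMB non-serious events by arm, and the stopping guideline names only SAEs.

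**Section 8.1.3 grades severity, not seriousness.** Correct, and it covers only events outside CTCAE. The two sections do not formally contradict each other. The wording is confusing and should be reconciled, but the point does not depend on it.

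**Some examples are really about the ICU clause.** A life-threatening embolism treated on a ward is excluded only by that clause, and clarifying the clause would bring it in. This stands, so the point is limited to events that are not life-threatening.

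**Relapse is captured elsewhere.** A return to oxygen for more than a day counts as clinical relapse. That is an efficacy endpoint, and it misses readmission without oxygen.

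**Conclusion.** The gap is real and worth closing. As written, the definition leaves three kinds of event, when not caused by COVID-19 progression and not life-threatening, outside the DSMB's SAE list, the stopping guideline and immediate reporting. They still reach the sponsor as non-serious events if Grade III or above, so this weakens harm detection but does not remove it.

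Two stronger readings are not supported. One is that none of the programme's earlier drug-related SAEs would count here. That is clear for the ventricular tachycardia and only very likely for the hyperglycemia, whose exact grade and ICU status are not given. Part of the Phase IIa safety text was not available to check. The other is that a number of missed events can be stated, which would need readmission rates that the documents do not contain.

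The conclusion rests on reading the list in 8.1.2 as closed and on the charter not promising more than the protocol does. If the charter already gives the DSMB all Grade III and above events by arm, the visibility part largely falls away for those events. The stopping guideline and reporting parts remain. SAE frequencies in this trial are also not on the same basis as in Phase I, as the ventricular tachycardia shows.

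**What to change.** Extend Section 8.1.2 so that an adverse event is also serious if, for a reason other than COVID-19 progression, it:

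- leads to readmission or prolongs the hospital stay;
- results in persistent or significant disability; or
- is medically important in the judgement of the investigator or sponsor.

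Apply the extended definition to reporting in 8.3, the SAE summary in 10.4.4, and the DSMB list and stopping guideline in 10.5. State in 8.1.1, 8.1.6 and 8.2 that SAEs are collected whatever their grade. Without this, rewording 8.1.2 alone might not recover an event such as the mild ventricular tachycardia. In the same edit, say what the ICU clause qualifies, align the Grade 3 wording in 8.1.3, and specify the adverse event content of the CRO reports in 11.5.

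The cost is protocol and safety-plan wording, more SAE forms and a longer DSMB list. Events of Grade III and above are already collected, so new data are needed only for a few lower-grade SAEs. Limiting the new criteria to causes other than COVID-19 progression keeps the expected course of disease from filling the list.
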